5.2 Pre-treatment Criteria

5.2.1 Screening for trial eligibility

Day -28 to Day 1: Screening Visit

Eligibility and exclusion criteria are provided in Section 3. These criteria will be assessed within 28 days of the first dose of study treatment (Pembrolizumab) to establish eligibility and baseline values.

Informed consent will be obtained after the study has been fully explained to the subject and before the conduct of any screening procedures or assessments. If screening assessments occur within 3 days before start of study treatment, then they may serve as the baseline Cycle 1 Day 1 visit and cycle 1 day 1 labs do not need to be performed.

Demographic information and baseline characteristics will be collected at the Screening Visit. Standard demographic parameters include age, sex, and race/ethnicity (recorded in accordance with prevailing regulations). Baseline characteristics will include ECOG PS (Appendix A), disease status, medical histories, and prior and concomitant medications. P16 / HPV status will also be collected when available.

Additional testing required, as per Section 3, is: hematology panel (see Table 2), chemistry panel (see Table), coagulation panel, urine or serum HCG (in women of childbearing potential; see Section 3 for when serum HCG testing is required), TSH, and EKG.

Patients will also need to undergo a radiation planning appointment prior to the start of treatment.

Archival tumor sample should be collected (block or if not possible, 20 unstained slides) from both most recent biopsy, as well as any tumor tissue obtained prior to starting initial PD-1 or PD-L1 directed therapy, if available. If a tumor deposit is safely accessible, a baseline tumor biopsy is also suggested. A second optional biopsy will be repeated if a tumor remains accessible (close to the end of cycle 2, and within 14 days before the third cycle of pembrolizumab).

Further details about collection and handling of tumor biopsy specimen can be found in Section 9 and appendices.

Table 2: Clinical Laboratory tests:

Category	Tests
Hematology panel	
• Hematocrit, hemoglobin, platelet count, WBC with differential (bands, basophils, eosinophils, lymphocytes, monocytes, neutrophils), ANC
Chemistry Panel	
• Chloride, potassium, sodium, BUN, serum creatinine, phosphorus, calcium, albumin, total protein, alkaline phosphatase, ALT, AST, total bilirubin (NOTE: the frequency of checking magnesium levels is left up to the treating provider)

Abbreviations: ALT = alanine aminotransferase; ANC = absolute neutrophil count; AST = aspartate aminotransferase; β -hCG = beta-human chorionic gonadotropin; BUN = blood urea nitrogen; WBC = white blood cells, ANC=absolute neutrophil count

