6.2 Management of toxicities attributable to pembrolizumab

Adverse events (both non-serious and serious) associated with pembrolizumab exposure may represent an immunologic etiology. These adverse events may occur shortly after the first dose or several months after the last dose of treatment. Pembrolizumab must be withheld for drug-related toxicities and severe or life-threatening AEs as per Table 4 below.

Table 4: Dose modification guidelines for Pembrolizumab for drug-related adverse events

Toxicity	Hold Treatment For Grade	Timing for Restarting Treatment	Discontinue Subject
Diarrhea/Colitis	2-3	Toxicity resolves to Grade 0-1.	Toxicity does not resolve within 12 weeks of last dose or inability to reduce corticosteroid to 10 mg or less of prednisone or equivalent per day within 12 weeks.
	4	Permanently discontinue	Permanently discontinue
AST, ALT, or Increased Bilirubin	2	Toxicity resolves to Grade 0-1	Toxicity does not resolve within 12 weeks of last dose.
	3-4	Permanently discontinue (see exception below) ¹	Permanently discontinue
Type 1 diabetes mellitus (if new onset) or Hyperglycemia	T1DM or 3-4	Hold pembrolizumab for new onset Type 1 diabetes mellitus or Grade 3-4 hyperglycemia associated with evidence of beta cell failure.	Resume pembrolizumab when patients are clinically and metabolically stable.
Hypophysitis	2-3	Toxicity resolves to Grade 0-1	Toxicity does not resolve within 12 weeks of last dose or inability to reduce corticosteroid to 10 mg or

CONFIDENTIAL

This document is confidential. Do not disclose or use except as authorized.

Toxicity	Hold Treatment For Grade	Timing for Restarting Treatment	Discontinue Subject
			less of prednisone or equivalent per day within 12 weeks.
	4	Permanently discontinue	Permanently discontinue
Hyperthyroidism	3	Toxicity resolves to Grade 0-1	Toxicity does not resolve within 12 weeks of last dose or inability to reduce corticosteroid to 10 mg or less of prednisone or equivalent per day within 12 weeks.
	4	Permanently discontinue	Permanently discontinue
Hypothyroidism	2-4	Therapy with pembrolizumab can be continued while treatment for the thyroid disorder is instituted	Therapy with pembrolizumab can be continued while treatment for the thyroid disorder is instituted.
Infusion Reaction	3-4	Permanently discontinue	Permanently discontinue

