Subjects should be assessed for possible ECIs prior to each dose. Lab results should be evaluated and subjects should be asked for signs and symptoms suggestive of an immune-related event. Subjects who develop an ECI thought to be immune-related should have additional testing to rule out other etiologic causes. If lab results or symptoms indicate a possible immune-related ECI, then additional testing should be performed to rule out other etiologic causes. If no other cause is found, then it is assumed to be immune-related.

7.8.6 Definition of an Overdose of pembrolizumab for This Protocol and Reporting of Overdose to Merck

CONFIDENTIAL

This document is confidential. Do not disclose or use except as authorized.

For purposes of this trial, an overdose of pembrolizumab will be defined as any dose of 1,000 mg or greater. No specific information is available on the treatment of overdose of pembrolizumab. Appropriate supportive treatment should be provided if clinically indicated. In the event of overdose, the subject should be observed closely for signs of toxicity. Appropriate supportive treatment should be provided if clinically indicated.

If an adverse event(s) is associated with (“results from”) the overdose of a Merck product, the adverse event(s) is reported as a serious adverse event, even if no other seriousness criteria are met.

If a dose of Merck’s product meeting the protocol definition of overdose is taken without any associated clinical symptoms or abnormal laboratory results, the overdose is reported as a non-serious Event of Clinical Interest (ECI), using the terminology “accidental or intentional overdose without adverse effect.”

All reports of overdose with and without an adverse event must be reported within 24 hours to the Sponsor and within 2 working days hours to Merck Global Safety. (Attn: Worldwide Product Safety; [contact])

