APPENDIX B: Pembrolizumab Events of Clinical Interest

Pneumonitis (reported as ECI if ≥ Grade 2)		
Acute interstitial pneumonitis	Interstitial lung disease	Pneumonitis
Colitis (reported as ECI if ≥ Grade 2 or any grade resulting in dose modification or use of systemic steroids to treat the AE)		
Intestinal Obstruction	Colitis	Colitis microscopic
Enterocolitis	Enterocolitis hemorrhagic	Gastrointestinal perforation
Necrotizing colitis	Diarrhea	
Endocrine (reported as ECI if ≥ Grade 3 or ≥ Grade 2 and resulting in dose modification or use of systemic steroids to treat the AE)		
Adrenal Insufficiency	Hyperthyroidism	Hypophysitis
Hypopituitarism	Hypothyroidism	Thyroid disorder
Thyroiditis	Hyperglycemia, if ≥Grade 3 and associated with ketosis or metabolic acidosis (DKA)	
Endocrine (reported as ECI)		
Type 1 diabetes mellitus (if new onset)		
Hematologic (reported as ECI if ≥ Grade 3 or any grade resulting in dose modification or use of systemic steroids to treat the AE)		
Autoimmune hemolytic anemia	Aplastic anemia	Thrombotic Thrombocytopenic Purpura (TTP)
Idiopathic (or immune) Thrombocytopenia Purpura (ITP)	Disseminated Intravascular Coagulation (DIC)	Haemolytic Uraemic Syndrome (HUS)
Any Grade 4 anemia regardless of underlying mechanism		
Hepatic (reported as ECI if ≥ Grade 2, or any grade resulting in dose modification or use of systemic steroids to treat the AE)		
Hepatitis	Autoimmune hepatitis	Transaminase elevations (ALT and/or AST)
Infusion Reactions (reported as ECI for any grade)		
Allergic reaction	Anaphylaxis	Cytokine release syndrome
Serum sickness	Infusion reactions	Infusion-like reactions
Neurologic (reported as ECI for any grade)		
Autoimmune neuropathy	Guillain-Barre syndrome	Demyelinating polyneuropathy
Myasthenic syndrome		
Ocular (report as ECI if ≥ Grade 2 or any grade resulting in dose modification or use of systemic steroids to treat the AE)		
Uveitis	Iritis	
Renal (reported as ECI if ≥ Grade 2)		
Nephritis	Nephritis autoimmune	Renal Failure
Renal failure acute	Creatinine elevations (report as ECI if ≥Grade 3 or any grade resulting in dose modification or use of systemic steroids to treat the AE)	
Skin (reported as ECI for any grade)		
Dermatitis exfoliative	Erythema multiforme	Stevens-Johnson syndrome
Toxic epidermal necrolysis		
Skin (reported as ECI if ≥ Grade 3)		
Pruritus	Rash	Rash generalized
Rash maculo-papular		
Any rash considered clinically significant in the physician's judgment		
Other (reported as ECI for any grade)		

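### The itemised chemistry panel omits glucose and bicarbonate, so the protocol's own diabetes and hyperglycemia hold and ECI rules rest on symptoms and unscheduled tests

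*Combined protocol and SAP*

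**What the plan says.** Section 5.2.1, Table 2, defines the chemistry panel by listing its contents: "Chloride, potassium, sodium, BUN, serum creatinine, phosphorus, calcium, albumin, total protein, alkaline phosphatase, ALT, AST, total bilirubin". Footnote d to the Study Calendar (Section 10, Table 8) repeats the list. Both add one note, that "the frequency of checking magnesium levels is left up to the treating provider"; no other analyte is left to discretion.

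Three other places set rules about glucose metabolism:

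- Section 6.2, Table 4: "Hold pembrolizumab for new onset Type 1 diabetes mellitus or Grade 3-4 hyperglycemia associated with evidence of beta cell failure". Restarting is tied to metabolic state: "Resume pembrolizumab when patients are clinically and metabolically stable".
- Appendix B: new-onset type 1 diabetes is an ECI, and so is "Hyperglycemia, if ≥Grade 3 and associated with ketosis or metabolic acidosis (DKA").
- Section 7.8.5: "Subjects should be assessed for possible ECIs prior to each dose. Lab results should be evaluated". The same sentence goes on to require that patients be asked about signs and symptoms. Further testing follows if either laboratory results or symptoms point to an immune-related event. ECIs go to the Sponsor within 24 hours and to Merck within 2 working days.

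The supportive-care part of Section 6.2 has an entry for type 1 diabetes and hyperglycemia with no instruction beneath it. Section 13.5 reports the incidence of each toxicity, by maximum CTCAE grade, with 90% exact intervals.

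**The concern.** The protocol tells sites to act on a metabolic toxicity and to look for it in laboratory results before each dose, but schedules no laboratory test that would show it. Because the panel is itemised, a site that orders exactly what is listed has complied in full and holds no glucose value, at baseline or later.

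Two things are at stake. The first is safety: the hold and ECI rules can start only from a symptom or a test ordered for another reason, so hyperglycemia without symptoms can go unnoticed. The second is the safety analysis. Under Section 13.6 a patient with no recorded adverse event still counts as assessed, so a patient whose glucose was never measured stays in the Section 13.5 denominator as if free of hyperglycemia.

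**Working it through.** No formula applies and the plan gives no figure to reproduce. The check compares every scheduled test with the rules that need a result.

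**Step 1: the panel.** Counting Table 2: chloride, potassium, sodium, BUN, creatinine (5); phosphorus, calcium, albumin, total protein (9); alkaline phosphatase, ALT, AST, total bilirubin (13). Glucose or bicarbonate: 0 of 13. Footnote d of Table 8: the same 13, again 0.

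**Step 2: could this be a lost table row?** The abbreviations under Table 2 include β-hCG, which is in neither row shown, so a row may have been lost in text extraction. That does not explain the omission, because footnote d states the chemistry list separately and is complete in itself.

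**Step 3: the other scheduled tests.** Sections 4.3, 5.2.1, 5.3 and 10 and Appendix J add hematology, PT/PTT, pregnancy test, TSH, HIV test and EKG. The every-3-week heading in Section 5.3 mentions urine, but the items under it are hematology, chemistry and TSH. No glucose, HbA1c, urinalysis or ketone test is scheduled.

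**Step 4: rules against tests.**

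| Rule | What it needs | Scheduled laboratory test |
|---|---|---|
| Table 4, liver | AST, ALT, bilirubin | Yes, each cycle |
| Table 4, renal | Creatinine | Yes, each cycle |
| Table 4, thyroid | Thyroid function | TSH, every 3 cycles |
| Table 4, type 1 diabetes or hyperglycemia | Glucose, then evidence of beta cell failure | None |
| Appendix B, hyperglycemia ECI | Glucose, plus ketosis or metabolic acidosis | None |
| Table 4, restart after diabetes or hyperglycemia | Metabolic stability | None |

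**Step 5: what remains.** Detection can still come from the symptom enquiry before each dose, from the adverse event review, weight, vital signs and physical examination each cycle, and from unscheduled tests. These can find symptomatic cases. They give no systematic route to asymptomatic hyperglycemia.

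**Step 6: baseline.** Section 5.2.1 collects medical history and medications, so known diabetes is identified. Exclusion 12 does not exclude patients on insulin replacement, but their treatment would be on record. What the schedule cannot show is hyperglycemia that is present but undiagnosed at entry.

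**Step 7: direction of the effect on Section 13.5.** Missed cases lower the numerator and leave the denominator unchanged, so incidence is under-ascertained to the extent that cases are missed. The documents give no rate from which to size this.

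**The case against.** The best defence is that the protocol deliberately uses symptoms followed by work-up for immune events. Section 7.8.5 pairs laboratory review with symptom enquiry and calls for further testing on either. Hypophysitis and myocarditis have Table 4 hold rules, and adrenal insufficiency and pancreatitis are ECIs, with no dedicated scheduled blood test; the EKG is at screening only. The ECI guidance document cited in Sections 6.2 and 7.8.5 covers identification and evaluation and may say more. It is not available here.

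Much of this stands. A reader might infer that the hold and ECI rules cannot operate at all, or not before ketoacidosis. The documents do not support that: symptom-led detection is written in. Nor would an isolated high glucose meet either hyperglycemia rule, since one also requires evidence of beta cell failure and the other ketosis or acidosis. It is also wrong to say that this toxicity alone lacks a scheduled test. The contrast in the table holds only against the liver, renal and thyroid rules. The unseen guidance limits the point to the protocol's own schedule.

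The mismatch survives. The protocol itemises its panel, leaves only magnesium to the provider, and asks for laboratory review before each dose. That some other events also lack a dedicated test does not supply a glucose result. Local panels may include glucose, but the protocol neither requires nor collects it.

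**Conclusion.** The gap is real, and modest. It covers each scheduled chemistry panel, from screening onward, for up to 26 patients (Section 13.2). Its consequence is that asymptomatic or previously undiagnosed hyperglycemia can be missed and that the reported incidence may be too low. Eligibility, the day-1 criteria to treat and the primary endpoint do not use glucose. The conclusion assumes that sites order what the tables list and that no unseen document adds the tests.

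Several stronger readings are tempting but unsupported:

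- That new-onset disease cannot be told from pre-existing disease. This goes too far: history and medications identify known diabetes.
- That hyperglycemia incidence would merely reflect which sites measure glucose. The documents say nothing about site practice.
- That steroid use enlarges the problem. Section 5.6.1 permits steroids for radiation symptoms but says nothing about their effect on glucose.
- That run-in decisions are at risk. Section 5.5 exempts Grade 3 asymptomatic endocrinopathy from the DLT definition, and no rate is given for events outside that exemption.

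The frequency of these events in this population also cannot be taken from the protocol. The 60-patient head and neck cohort summarised in Section 2.1.1.2 names neither diabetes nor hyperglycemia among the events it lists.

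**What to change.** Reconcile Table 2 and Table 8 footnote d with Table 4, the empty diabetes and hyperglycemia entry in Section 6.2, the pre-dose ECI check in Section 7.8.5, and Appendix B. The simplest way is to add glucose and bicarbonate to the listed panel, measured at screening and on day 1 of each cycle and collected on the CRF. The cost is small: two analytes on blood already drawn, two CRF fields and matching edits to the two lists, with no extra visit or blood draw. Evidence of beta cell failure and ketosis would still need follow-up testing when a result or symptom prompts it.

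If the sponsor means detection to be symptom-led, the protocol should say so, and the Section 13.5 report should describe hyperglycemia as clinically detected. The content of the hold and restart rules is for the sponsor and is not addressed here.

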5.3 On treatment visits

Reasonable effort should be made to conduct study visits on the day scheduled (+/- 3 days).

Patients will also see the treating radiation oncologist as they are receiving radiation as per standard clinical practice.

Any changes from screening clinical evaluation findings that meet the definition of an AE will be recorded on the AE page of the eCRF.

Cycle 1, Day 1

If screening assessments occur within 3 days before start of study treatment, then they may serve as the baseline Cycle 1 Day 1 visit and screening tests do not need to be repeated.

Draw blood sample for:

- Hematology panel (Table 2)
- Chemistry panel (Table 2)

Record:

- ECOG PS
- Weight
- Vital signs
- Physical exam
- Concomitant medication use

CONFIDENTIAL

This document is confidential. Do not disclose or use except as authorized.

Review all laboratory results before administering study treatment.

Criteria to treat at cycle 1 day 1:

- **Absolute neutrophil count $\geq 1000/\mu\text{l}$**
- **Platelets $\geq 75,000/\mu\text{l}$**
- **ALT and AST $\leq 3.0 \times \text{ULN}$ in a patient with no documented liver metastases; ALT and AST $\leq 5.0 \times \text{ULN}$ in a patient with documented liver metastases**
- **Total bilirubin $\leq 1.5 \times \text{ULN}$ ($2.0 \times \text{ULN}$ in a patient with well documented Gilbert's syndrome)**

Every-3-week assessments, day 1 of every cycle:

The following assessments should be performed on the indicated weeks.

Draw blood/collect urine sample for:

- Hematology panel
- Chemistry panel
- TSH (every 3 cycles)

Record:

- ECOG PS
- Weight
- Vital signs
- Physical exam
- Concomitant medication use
- AEs or SAEs

Criteria to treat at day 1:

- **Absolute neutrophil count $\geq 1000/\mu\text{l}$**
- **Platelets $\geq 75,000/\mu\text{l}$**
- **ALT and AST $\leq 3.0 \times \text{ULN}$ in a patient with no documented liver metastases; ALT and AST $\leq 5.0 \times \text{ULN}$ in a patient with documented liver metastases**
- **Total bilirubin $\leq 1.5 \times \text{ULN}$ ($2.0 \times \text{ULN}$ in a patient with well documented Gilbert's syndrome)**

Review all laboratory results before administering study treatment.

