9. Ability to understand and the willingness to sign a written informed consent document
10. Female subjects of childbearing potential must have a negative serum pregnancy test at screening.
11. Female and male subjects of childbearing potential must agree to use an adequate method of contraception as outlined in section 5.7.1. Contraception is required prior to study entry and for the duration of study participation and 4 months after completion of pembrolizumab administration.
 - Note: Abstinence is acceptable if this is the usual lifestyle and preferred contraception for the subject.
12. Participants must have normal organ and marrow function as defined below:
 - leukocytes $\geq 3,000/\text{mcL}$
 - absolute neutrophil count $\geq 1,500/\text{mcL}$
 - platelets $\geq 100,000/\text{mcL}$

CONFIDENTIAL

This document is confidential. Do not disclose or use except as authorized.

- hemoglobin ≥ 9 g/dl
- total bilirubin $\leq 1.5 \times$ institutional upper limit of normal (ULN)
- AST(SGOT)/ALT(SGPT) $\leq 2.5 \times$ institutional ULN
- AST(SGOT)/ALT(SGPT) For patients with documented liver metastases, $\leq 5 \times$ institutional ULN
- creatinine $\leq 1.5 \times$ within normal institutional ULN

OR

- creatinine clearance ≥ 60 mL/min/1.73 m² for participants with creatinine levels above institutional ULN.
- International normalized ratio (INR) or Prothrombin Time (PT) < 1.5 times the upper limit of normal unless subject is receiving anticoagulant therapy, as long as PT or PTT is within therapeutic range of intended use of anticoagulants.
- Activated Partial Thromboplastin Time (aPTT) < 1.5 times the upper limit of normal unless subject is receiving anticoagulant therapy, as long as PT or PTT is within therapeutic range of intended use of anticoagulants.

Laboratory tests required for eligibility must be completed within 14 days prior study entry. Baseline tumor measurements must be documented from tests within 28 days of study entry. Other non-laboratory tests must be performed within 28 days of study entry.

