- Liver transaminase elevation \leq 8 times ULN that downgrades to Grade \leq 2 (\leq 5 times ULN) within 7 days after onset, whereby maximal supportive care, including systemic corticosteroids, is permitted.
- Total bilirubin \leq 5 times ULN that downgrades to Grade \leq 2 (\leq 3 times ULN) within 7 days after onset, whereby maximal supportive care, including systemic corticosteroids, is permitted.
- Grade \geq 3 neutropenia that (1) is not associated with fever or systemic infection, (2) does not require medical intervention, and (3) improves to Grade 2 within 7 days.
- Grade 3 and 4 lymphopenia.
- Grade 3 thrombocytopenia that (1) is not associated with clinically significant bleeding, (2) does not require medical intervention, and (3) improves to Grade 2 within 7 days.
- Isolated Grade 3 electrolyte abnormalities that are not associated with clinical signs or symptoms and are reversed with appropriate maximal medical intervention within 3 days.
- Any pre-existing laboratory abnormality that deteriorates to Grade 3/4, but where the increment of deterioration is considered not clinically significant by both investigator and sponsor.

Immune-related AEs (irAEs) are defined as AEs of immune nature (i.e., inflammatory) in the absence of a clear alternative etiology. In the absence of clinical abnormality, repeat laboratory testing will be conducted to confirm significant laboratory findings prior to designation as a DLT.

While rules for adjudicating DLTs are specified above, an AE that is Grade $<$ 3 or listed as exempt above may also be defined as a DLT after consultation with the sponsor and Investigators, based on the emerging safety profile of pembrolizumab. Likewise, subjects who become not evaluable for DLT because they discontinued or interrupted treatment due to toxicities other than DLTs may be counted as DLT subjects.

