Myocarditis	1-2	Toxicity resolves to 0	Toxicity does not resolve within 12 weeks of last dose or inability to reduce corticosteroid to 10 mg or less of prednisone or equivalent per day within 12 weeks.
	3-4	Permanently discontinue	Permanently discontinue
Pneumonitis	2	Toxicity resolves to Grade 0-1	Toxicity does not resolve within 12 weeks of last dose or inability to reduce corticosteroid to 10 mg or less of prednisone or equivalent per day within 12 weeks.
	3-4	Permanently discontinue	Permanently discontinue
Renal Failure or Nephritis	2	Toxicity resolves to Grade 0-1	Toxicity does not resolve within 12 weeks of last dose or inability to reduce corticosteroid to 10 mg or less of prednisone or equivalent per day within 12 weeks.
	3-4	Permanently discontinue	Permanently discontinue

CONFIDENTIAL

This document is confidential. Do not disclose or use except as authorized.

Toxicity	Hold Treatment For Grade	Timing for Restarting Treatment	Discontinue Subject
All Other Drug-Related Toxicity ²	3 or Severe	Toxicity resolves to Grade 0-1	Toxicity does not resolve within 12 weeks of last dose or inability to reduce corticosteroid to 10 mg or less of prednisone or equivalent per day within 12 weeks.
	4	Permanently discontinue	Permanently discontinue

Note: Permanently discontinue for any severe or Grade 3 drug-related AE that recurs or any life-threatening event.

¹ For patients with liver metastasis who begin treatment with Grade 2 AST or ALT, if AST or ALT increases by greater than or equal to 50% relative to baseline and lasts for at least 1 week then patients should be discontinued.

² Patients with intolerable or persistent Grade 2 drug-related AE may hold study medication at physician discretion. Permanently discontinue study drug for persistent Grade 2 adverse reactions for which treatment with study drug has been held, that do not recover to Grade 0-1 within 12 weeks of the last dose.

Supportive care for pembrolizumab toxicity, particularly suspected immune-mediated toxicity

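### For patients with liver metastases, above all those who enter with Grade 2 AST/ALT, the rules for treating, holding, restarting and stopping pembrolizumab do not fit together

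*Combined protocol and SAP*

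**What the plan says.** Four places in the protocol set rules on AST/ALT for these patients, and a fifth fixes a grade boundary.

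- **Entry (Section 3.1, criterion 12).** "For patients with documented liver metastases" the limit is 5 x ULN.
- **Day-1 treatment criteria (Section 5.3), for cycle 1 and every later cycle.** ALT and AST may be up to 5.0 x ULN "in a patient with documented liver metastases", and up to 3.0 x ULN "in a patient with no documented liver metastases". Neither limit mentions cause or change from baseline.
- **Table 4 (Section 6.2).** The text before the table reads: "Pembrolizumab must be withheld for drug-related toxicities and severe or life-threatening AEs as per Table 4 below". The table title limits it to drug-related events. In the row "AST, ALT, or Increased Bilirubin", Grade 2 is held until Grade 0-1, and the patient is discontinued if this is not reached within 12 weeks of the last dose. The Grade 2 line makes no provision for liver metastases or for a Grade 2 start. The Grade 3-4 line reads "Permanently discontinue (see exception below" and points to footnote 1.
- **Footnote 1 to Table 4.** It begins "For patients with liver metastasis who begin treatment with Grade 2 AST or ALT" and calls for discontinuation when AST or ALT is at least 50% above baseline for at least one week.
- **Hepatic guidance (Section 6.2, supportive care).** For Grade 2 events, liver tests are followed more often until they are back at baseline.

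Section 5.5, on dose-limiting toxicity, equates Grade 2 or lower transaminases with at most "5 times ULN) within 7 days after onset". This puts the top of Grade 2 at 5 x ULN. The lower edge of Grade 2 is not printed.

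**The concern.** The rules use three different yardsticks: an absolute multiple of ULN (3.1 and 5.3), a CTCAE grade (Table 4) and a percentage rise from the patient's own baseline (footnote 1). The hepatic guidance adds baseline as an endpoint for monitoring. The rules are not cross-referenced, and the protocol expressly admits the patients for whom they diverge.

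The first stake is safety: two sites could handle the same liver values differently while each follows a written rule. The second is the safety summary, because drug exposure and discontinuations for toxicity would depend partly on which section a site applied. There may also be a link to the run-in. Section 5.5 allows patients who become non-evaluable through interruption or discontinuation for other toxicity to be counted as having a DLT, and Section 13.1 ends the study at two DLTs in the run-in. That counting is discretionary, so this is a possible route and not a predicted effect.

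**Working it through.** There is no planned figure to reproduce. The check applies each rule to the same values, all in multiples of ULN.

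**Inputs.** Day-1 limit with liver metastases: 5.0 (5.3). Entry limit with liver metastases: 5 (3.1). Top of Grade 2: 5 (5.5). Footnote trigger: 1.5 x baseline for at least a week (Table 4, footnote 1). Bottom of Grade 2: assumed 3.0, with 2.5 shown as the other end of the range.

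**Step 1: treat versus hold.** Section 5.3 is passed at any value up to 5.0. Table 4's Grade 2 hold covers values above 3.0 and up to 5.0 if drug-related. The overlap is therefore the whole Grade 2 band, on condition that the rise is attributed to the drug. Without liver metastases the day-1 limit of 3.0 equals the assumed lower edge, so there is no overlap. With 2.5 as the edge, the overlap there would be 2.5 to 3.0.

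**Step 2: restart level against entry level.** Take entry at 4.0 and a drug-related rise to 4.8.
- Rise: 0.8/4.0 = 20%, still Grade 2.
- Section 5.3: passed, since 4.8 is below 5.0.
- Table 4: hold until Grade 0-1, that is 3.0 or less, which is (4.0 - 3.0)/4.0 = 25% below the entry value. With 2.5 as the edge it is 1.5/4.0 = 37.5% below.
- Hepatic guidance: monitor until back at 4.0.

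For entry at 5.0, the restart level is 2.0/5.0 = 40% below entry (50% with an edge of 2.5). A patient who returns exactly to the entry value meets the monitoring endpoint and the day-1 limit, but not the Table 4 restart level, and would be discontinued at 12 weeks.

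**Step 3: the footnote gap.** The trigger 1.5 x baseline exceeds 5.0 when baseline exceeds 5.0/1.5 = 3.33.

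| Baseline | Footnote trigger | Values above 5.0 and below the trigger |
|---|---|---|
| 3.4 | 5.1 | 5.0 to 5.1 |
| 4.0 | 6.0 | 5.0 to 6.0 |
| 4.5 | 6.75 | 5.0 to 6.75 |
| 5.0 | 7.5 | 5.0 to 7.5 |

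A move from 4.0 to 5.5 is a rise of 1.5/4.0 = 37.5%. It is above Grade 2, fails 5.3 and does not meet the footnote trigger. The Grade 3-4 line says stop but defers to the exception. The exception says when to stop and is silent on holding or restarting below its trigger. If 5.3 fills the silence, this patient could resume at 5.0 or below, while the patient who rose only to 4.8 must reach Grade 0-1. If the Grade 3-4 line fills it, the patient stops permanently.

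**Step 4: where all three outcomes meet.** This needs a Grade 2 baseline and a current value of at least 1.5 x baseline but no more than 5.0. The baseline must then lie between 3.0 and 3.33, and the value between 1.5 x 3.0 = 4.5 and 5.0, for at least a week. Example: 3.2 rising to 1.5 x 3.2 = 4.8. With an edge of 2.5 the window is baseline 2.5 to 3.33 and value 3.75 to 5.0. It also requires reading a footnote marked on the Grade 3-4 line as covering Grade 2 values.

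**The case against.** The best defence is scope. Table 4 concerns drug-related events, whereas 5.3 is a general laboratory check whatever the cause. Section 5.1 sends dose modifications to Section 6, 6.1 says that pembrolizumab is held as directed for toxicity attributed to it, and the supportive-care text in 6.2 ties its guidance to events that the investigator judges related. Read together, a patient must pass 5.3 and also have no drug-related hold. On that reading, a patient who began at Grade 0-1 and has a drug-related rise to 4.5 x ULN is held, and passing the day-1 limit does not override that. A lower limit for not dosing today and a higher, sustained limit for stopping for good can also be a graded scheme, with 5.3 reapplied each cycle.

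Much of this stands. The joint reading is reasonable and largely answers Step 1, although 5.3 itself does not state it. It also rules out a stronger reading that a reader might infer: that one AST/ALT value leads generally to dosing, holding or permanent stop. Outcomes depend on attribution, baseline and duration, and Step 4 shows how small the common window is. Every trigger in the Step 3 table lies above 5.0, where 5.3 already bars dosing, so none of them shows one rule dosing while another stops.

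A reader might also size the problem as one patient in 19. The documents do not support that. Nineteen is the efficacy decision number in 13.1, the safety summaries in 13.5 and 13.6 use treated patients with a safety assessment, and nothing says how many patients will have liver metastases or Grade 2 values at entry.

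The joint reading does not cure Steps 2 and 3. Both remain when every event is agreed to be drug-related.

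**Conclusion.** The inconsistency is real but narrower than a general three-way contradiction. For patients with liver metastases admitted at Grade 2, Table 4 sets a restart level below their entry value, while the hepatic guidance looks to baseline and 5.3 to 5.0 x ULN. For baselines above 3.33 and up to 5.0 x ULN, drug-related values above 5.0 and below 1.5 x baseline have no clear instruction, although a smaller Grade 2 rise has a strict one. The missing link between 5.3 and Table 4 is a lesser, drafting-level gap.

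The 3.33 threshold and the Step 3 gaps rest only on printed figures. The distance to the restart level and the Step 4 window depend on the assumed lower edge of Grade 2 (3.0, range 2.5 to 3.0). The number of patients affected cannot be estimated from the documents. The sample size, the two-stage decision rule and the primary analysis calculation do not depend on this point. It merits correction because it concerns safety and is cheap to resolve.

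**What to change.** Reconcile Section 5.3, the Table 4 AST/ALT row, footnote 1 and the hepatic guidance in Section 6.2 in one clarifying amendment. For patients with liver metastases, state once, by baseline grade and by attribution, which text governs treating, holding, restarting and stopping, and have the other places refer to it. The amendment should:

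- say in 5.3 how its limits relate to a drug-related hold under Table 4;
- say what counts as return for a patient who entered at Grade 2;
- say whether footnote 1 replaces or adds to the Grade 3-4 entry, whether it reaches Grade 2 values, and what applies above 5.0 x ULN but below its trigger;
- say which of the attribution categories in Section 7.2 count as drug-related for Table 4.

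The limits themselves are for the clinical team. The cost is one amendment and site notification, with no extra tests, visits or patients.
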